14.3 Vital Signs

Vital signs are assessed at Screening, Day -1 predose, and on Day 1 every 2 hours for the first 6 hours after the initial dose; vital signs then to be evaluated every 6 hours thereafter until Day 4 (EOT).

Vital signs will be summarized using descriptive statistics at Baseline and all scheduled post-Baseline visits/timepoints. The change from Baseline values will also be summarized at the scheduled post-Baseline visits/timepoints.

Vital sign values will be considered PCI if they meet the criteria listed in [Table 6](#). The number and percentage of subjects with post-Baseline vital signs that are PCI will be summarized by treatment group at each post-Baseline visit and for overall post-Baseline. For the overall post-Baseline summaries, all post-Baseline values will be considered, including unscheduled and out of window values. Subjects with multiple PCI values for a given parameter will be counted only once for that parameter. For the by-visit summary, the numerator for the percentage is the number of subjects with a post-Baseline PCI vital sign for the given parameter, visit and treatment group, and the denominator is the number of subjects with non-missing values for the given parameter, visit and treatment group. For the overall

post-Baseline summary, the numerator for the percentage is the number of subjects with at least 1 post-Baseline PCI vital sign for the given parameter and treatment group, and the denominator is the number of subjects with at least 1 post-Baseline vital sign for the given parameter and treatment group. A listing of overall and of subjects with any PCI vital sign values will be provided.

Table 6 Criteria for Potentially Clinically Important Vital Signs

Vital Sign Parameter	Unit	Criteria ^a		
		Observed Value	And/Or	Change Relative to Baseline
Systolic blood pressure (supine or sitting)	mmHg	≥180	And	Increase of ≥20
		≤90	And	Decrease of ≥20
Diastolic blood pressure (supine or sitting)	mmHg	≥105	And	Increase of ≥15
		≤50	And	Decrease of ≥15
Pulse (supine or sitting)	bpm	≥120	And	Increase of ≥15
		≤50	And	Decrease of ≥15

^a A post-baseline value is considered as a PCI value if it meets both criteria for observed value and change from baseline.

14.4 Electrocardiogram (ECG)

12-lead ECGs are collected at Screening, Day -1 predose, Days 1 through 3 (at 1 hour postdose), and EOT/ET. Observed values of ECG variables (e.g., heart rate, PR interval, QRS interval, QT interval, and QTc interval) and the changes from Day -1 (predose) at each assessment time point will be summarized by treatment group.

QTcB and QTcF will also be categorized into the following categories (msec) and the number and percentage of subjects in each category will be summarized by treatment group at each visit and for the overall post Day -1 dose maximum:

- Observed: ≤450, 451 - ≤480, 481 - ≤500, and >500; >450; >480.
- Change from Baseline: ≤10, 11 – 30, 31 – 60, and >60; >30.

For cardiologist's interpretations, the number and percentage of subjects with ECG results that are determined as normal or abnormal will be summarized at scheduled visits. The overall post-baseline worst interpretation will also be summarized (i.e. if a subject has one or more post-baseline ECG results that is/are considered as abnormal, this subject will be counted in the abnormal category). Cardiologist's interpretations will also be summarized in a shift table. The shifts from Baseline to overall post-Baseline worst interpretation will also be presented. For the by-visit shift summary, the denominator is the number of subjects with non-missing cardiologist's interpretation at Baseline and the given visit for the given treatment group. For the summaries of shift from Baseline to the overall post-Baseline worst interpretation, the denominator is the number of subjects with non-missing Baseline and at least 1 post-Baseline cardiologist's interpretation for the given treatment group.

Electrocardiogram variable values will be considered PCI if they meet the criteria listed in

Table 7. The number and percentage of subjects with post-baseline PCI values will be summarized by treatment group at each post-Baseline visit and for overall post-Baseline. For the by-visit summary, the numerator for the percentage is the number of subjects with a post-Baseline PCI ECG for the given parameter, visit and treatment group, and the denominator is the number of subjects with non-missing values for the given parameter, visit and treatment group. For the overall post-Baseline summary, the numerator for the percentage is the number of subjects with at least 1 post-Baseline PCI ECG for the given parameter and treatment group, and the denominator is the number of subjects with at least 1 post-Baseline ECG value for the given parameter and treatment group. A listing of overall and of all subjects with any PCI ECG values will be provided.

Table 7 Criteria for Potentially Clinically Important ECG Values

ECG Parameter	Unit	High PCI Criteria
QRS Interval	msec	≥120
PR Interval	msec	≥220
QTcB or QTcF	msec	>500
QTcB or QTcF: change from baseline	msec	>60

14.5 Physical Examination

Physical examinations are performed at Day -1 predose, Day 4, and at Follow-Up (surgical site only). Physical examination results (normal, abnormal, and not done) will be summarized in a frequency table by treatment group, body system and visit. A listing of overall physical examination data will be listed.

A listing related to surgical site inspection will be generated (Day 4 General Appearance, Day 7 Musculoskeletal). A shift table for surgical site inspection will be presented summarizing Day 4 and Day 7 and the shifts between the two visits (Abnormal Not Clinically Significant, Abnormal Clinically Significant).

14.6 Other Safety Variables

14.6.1 Suicidality Based on C-SSRS

The event counts and the number and percentage of subjects reporting any post Baseline suicidal ideation, suicidal behavior, or suicidality will be tabulated by treatment group. The event counts and the number and percentage of subjects reporting any post-Baseline non-suicidal self-injurious behavior will also be tabulated. For calculating the percentages, the denominator will be the number of subjects in the Safety Analysis Set.

15 CLINICAL PHARMACOKINETIC AND PHARMACODYNAMIC ANALYSES

All summary and analyses of PK or PD of ACP-044 will be performed for the PK Analysis Set based on the actual treatment group. The treatment groups will be ACP-044 400 mg Q6H and ACP-044 1600 mg QD.

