1.5.1 Rationale for Study Design

This is a Phase 2, randomized, double-blind, placebo-controlled inpatient study in subjects with acute postoperative pain following bunionectomy. The study will assess the efficacy of ACP-044 by comparing the same maximum dose of ACP-044, 1600 mg administered either as a single dose or as 400 mg administered every six hours. Guided by nonclinical animal models where ACP-044 provided robust analgesic effects when given prior to incision as a single dose or when administered daily at 24, 48, and 72 h post-incision, dosing in the present study will begin prior to surgery and will continue for 3 days after surgery.

Final Version: 1.0

Final Version: 1.0 Clinical Study Protocol Amendment 5 Date: 01 February 2022

1.5.2 **Rationale for Dose Selection**

In a nonclinical animal model, a single oral dose of ACP-044 prevented the development of incisional hyperalgesia for at least 3 days, with the highest dose tested (30 mg/kg) producing essentially complete prevention of hyperalgesia. Similarly, daily doses of ACP-044 given postincision provided continuous relief from an ongoing hyperalgesic insult in a dose-dependent manner. It is not clear, however, whether the response is driven by C_{max} or AUC. In the present proof of concept study, the maximum tolerated dose of ACP-044 is being evaluated by testing two dosing regimens (i.e., once-daily or every 6 hours) to allow the selection of the optimal dosing regimen and better characterization of the exposure-response relationship.

1.6 **Potential Risks and Benefits**

Nonclinical studies in animal models of acute and chronic nociception have demonstrated efficacy (i.e., analgesia) with ACP-044 and that it is safe and well tolerated. This study will help identify whether ACP-044 is efficacious as an analgesic treatment in humans as it is the first clinical efficacy study to date. If the study shows treatment with ACP-044 is effective, this could lead to further clinical development of this treatment for pain.

A detailed summary of the potential risks and benefits is available in the ACP-044 Investigator's brochure.

1.6.1 **Known Potential Risks**

In the Phase 1 clinical studies in healthy volunteers, the side effects that occurred in more than 1 subject treated with ACP-044 were indigestion and headache.

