2.6.1 Pharmacokinetic/Pharmacodynamic Endpoints

The PK/PD endpoints include:

- ACP-044 exposure-response relationship:
 - for efficacy using the primary endpoint, key secondary and selected secondary endpoints
 - o for safety using selected TEAEs

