9.4 Subject Populations for Analysis

The **Safety Analysis Set** includes all randomized subjects who received at least one dose of study drug (ACP-044 or placebo). Subjects will be analyzed based on the treatment that they actually received. The Safety Analysis Set will be used for all safety analyses.

The **Full Analysis Set** includes all randomized subjects who received at least one dose of study drug and who have undergone bunionectomy with at least one postoperative pain assessment. The Full Analysis Set will be used for the analysis of all efficacy endpoints.

The **Per-protocol (PP) Analysis Set** will consist of those subjects in the FAS who did not have any protocol deviations that could potentially have a substantial impact on the primary efficacy outcome. The precise reasons for excluding subjects from the PP Analysis Set will be fully defined and documented prior to the clinical database lock. Subjects will be analyzed

Final Version: 1.0

supportive analyses of selected efficacy endpoints.

Clinical Study Protocol Amendment 5 Date: 01 February 2022 based on their randomized treatment assignment. The PP Analysis Set will be used for

For ACP-044 plasma concentration summaries, the **Pharmacokinetics Analysis Set** will consist of subjects with at least one measurable ACP-044 plasma concentration.

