1 INTRODUCTION

This statistical analysis plan (SAP) provides a technical and detailed elaboration of the statistical analyses of safety and efficacy data as described in the study protocol Version 1.0 amendment 5 dated 01 February 2022.

Specifications for tables, figures, and listings are contained in a separate document. Statistical analyses for population pharmacokinetic (PK) and PK/pharmacodynamics (PD) modeling will be presented in a separate report and therefore will not be included in this SAP.

This plan should be read in conjunction with the study protocol and the electronic case report forms (eCRF).

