4 ANALYSIS SETS

Randomized Analysis Set

The Randomized Analysis Set includes all randomized subjects. Subjects will be analyzed based on their randomized treatment assignment.

Safety Analysis Set

The Safety Analysis Set includes all randomized subjects who received at least one dose of study drug (ACP-044 or placebo). Subjects will be analyzed based on the treatment that they actually received. The Safety Analysis Set will be used for all safety analyses.

Full Analysis Set

The Full Analysis Set includes all randomized subjects who received at least one dose of study drug post operation and who have undergone bunionectomy. Subjects will be analyzed based on their randomized treatment assignment. The Full Analysis Set will be used for the analysis of all efficacy endpoints.

Per-protocol Analysis Set

The Per-protocol (PP) Analysis Set includes all subjects in the Full Analysis Set who did not have any protocol deviations that could potentially have a substantial impact on the primary efficacy outcome. The precise reasons for excluding subjects from the PP Analysis Set will be fully defined and documented in a separate PD log file prior to the clinical database lock. Subjects will be analyzed based on their randomized treatment assignment. The PP Analysis Set will be used for supportive analyses of the primary efficacy endpoint.

Pharmacokinetics Analysis Set

The Pharmacokinetics Analysis Set includes all subjects with at least one measurable ACP-044 plasma concentration.

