15.2 Pharmacokinetic/Pharmacodynamic Endpoints

The PK/PD endpoints include:

- ACP-044 exposure-response relationship:
 - for efficacy using the primary endpoint and selected secondary endpoints
 - for safety using selected TEAEs

PK/PD endpoint summary and analysis will be discussed in a separate plan.

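### SAP Section 15, as written, would leave placebo out of the exposure-response analysis, although placebo is the only randomized contrast in total drug exposure

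*SAP*

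**What the plan says.** The opening rule of SAP Section 15 is "All summary and analyses of PK or PD of ACP-044 will be performed for the PK Analysis Set based on the actual treatment group". The next sentence reads "The treatment groups will be ACP-044 400 mg Q6H and ACP-044 1600 mg QD". SAP Section 4 defines the set: "The Pharmacokinetics Analysis Set includes all subjects with at least one measurable ACP-044 plasma concentration". A placebo subject dosed as assigned has no measurable concentration and so is not in it.

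Section 15 has two parts. Section 15.1 covers concentrations and already assigns their summary to the PK Analysis Set. Section 15.2 covers the exposure-response relationship for efficacy and for selected TEAEs.

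The protocol is narrower. Section 9.4 introduces the set with the words "For ACP-044 plasma concentration summaries". Protocol Section 9.5.8, which describes the population PK/PD model, names no analysis set.

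The modelling itself is deferred. SAP Section 1 says that population PK and PK/PD modelling "will be presented in a separate report and therefore will not be included in this SAP", Section 15.2 sends the PK/PD analysis to a separate plan, and Protocol Section 9.5.8 sends the results to a separate report.

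The endpoint lists also differ. SAP Section 15.2 has "for efficacy using the primary endpoint and selected secondary endpoints"; Protocol Section 2.6.1 has "for efficacy using the primary endpoint, key secondary and selected secondary endpoints". SAP Section 19 declares no changes from the protocol.

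**The concern.** Protocol Section 1.5.2 leaves open whether response is driven by Cmax or by AUC, and gives "better characterization of the exposure-response relationship" as one purpose of testing two regimens. The regimens were built with the same daily dose. That separates them on Cmax and makes them alike on AUC.

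The only group randomized to a different daily AUC is therefore placebo, at zero. Without it, any relation between drug AUC and pain or TEAEs is read from subjects who happened to clear the drug faster or slower. Those differences are not randomized and may travel with patient factors such as weight or renal function. The fitted curve also has no observed response at zero exposure, so within the model a flat line could mean no effect or a plateau.

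**Working it through.** **1. What the rule reaches.** Section 15.1 already places concentration summaries in the PK Analysis Set. The only PD content in Section 15 is the exposure-response work of Section 15.2. Taken literally, then, the mention of PD in the opening rule extends the set to exposure-response, which Protocol 9.4 does not do.

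**2. The plan's own figures.** The documents give no precision or power for exposure-response. The sample-size figures used below do reproduce. With a difference of 23 points, SD 50 and two-sided alpha 0.05 (Protocol 9.3, SAP 3.5), 76 per arm gives power 0.804 by t-test (0.809 by normal approximation). Then 76 / 0.95 = 80 per arm.

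**3. Daily drug AUC by arm.** Mean CL/F is 6.04 to 11.3 L/h and exposure is dose-proportional (Protocol 1.4.1). AUC over 24 h = daily dose / (CL/F).
- Once daily: 1600 / 11.3 = 142 to 1600 / 6.04 = 265 mg·h/L.
- Every 6 hours: 4 × 400 = 1600 mg, so the same 142 to 265 mg·h/L.

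The ratio between arms is 1.0.

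**4. Cmax by arm.** I used a one-compartment oral model at steady state, with half-life 1.6 to 3.2 h and Tmax 1 to 2 h (Protocol 1.4.1), and ka solved from Tmax. Per unit dose, C(t) is proportional to ka/(ka − k) × [e^(−kt)/(1 − e^(−kτ)) − e^(−ka·t)/(1 − e^(−ka·τ))], with τ = 24 h (dose 1600 mg) or 6 h (dose 400 mg). The once-daily to every-6-hours Cmax ratio is 3.62 and 3.23 (half-life 1.6 h, Tmax 1 and 2 h) and 2.85 and 2.67 (half-life 3.2 h). A Cmax contrast of roughly 2.7- to 3.6-fold survives without placebo.

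**5. Precision of a linear AUC slope (illustration).** Assumptions: 80 per arm, all evaluable; response linear in drug AUC; equal mean AUC in the active arms, scaled to 1; residual SD 50; slope of 23 points per mean exposure. The between-subject CV of drug AUC is assumed at 20% to 50%, because the documents give only a range of mean CL/F.

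- Active only: S₁ = 2n·CV² = 160·CV².
- Placebo added at 0: S₂ = 3n·(2/9) + 2n·CV² = 53.33 + 160·CV².
- SE of slope = 50/√S; SE ratio = √(S₂/S₁); power = Φ(23√S/50 − 1.96).

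| CV | S₁ | S₂ | SE active only | SE with placebo | SE ratio | Power active only | Power with placebo |
|---|---|---|---|---|---|---|---|
| 20% | 6.4 | 59.7 | 19.8 | 6.5 | 3.06 | 21% | 94% |
| 30% | 14.4 | 67.7 | 13.2 | 6.1 | 2.17 | 42% | 97% |
| 40% | 25.6 | 78.9 | 9.9 | 5.6 | 1.76 | 64% | 98% |
| 50% | 40.0 | 93.3 | 7.9 | 5.2 | 1.53 | 83% | 99% |

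The information lost by dropping placebo, 1 − S₁/S₂, runs from 1 − 6.4/59.7 = 89% to 1 − 40/93.3 = 57%.

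**The case against.** A reader might infer that the SAP has already settled the exclusion of placebo from exposure-response. The documents do not support that. SAP Section 1, SAP Section 15.2 and Protocol 9.5.8 all put the modelling elsewhere, and nothing says that Section 15 binds the separate plan. That plan was not supplied and may include placebo. A coherent reading also exists in which the opening rule governs only the concentration summaries, where two active arms is correct, and the mention of PD is loose drafting. This limits certainty but does not remove the problem. The rule is stated without exception, so a later plan must either follow it and lose placebo or contradict the SAP.

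A reader might also infer that an active-only analysis cannot address the AUC question at all. That too goes further than the documents allow. The Cmax contrast needs no placebo, and variation in clearance within arms still supports an AUC slope, though a weaker and observational one.

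Three further objections stand. Each active arm is compared with placebo on pain AUC0-24 in the Full Analysis Set, and TEAEs are tabulated by treatment group, so the placebo response is still reported and would help a reader interpret a flat active-only curve. Much of the precision gained from placebo is the drug-versus-no-drug contrast that the primary analysis already estimates. The table assumes a CV and a linear regression, whereas the protocol plans a population PK/PD model. The missing key secondary endpoints are a separate mismatch and lend no support to the placebo point.

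**Conclusion.** The concern holds in a limited form. As written, Section 15 prescribes for PD a population that the protocol reserves for concentration summaries. If the separate PK/PD plan follows it, exposure-response loses the only randomized contrast in daily drug AUC. That conclusion needs only the equal daily dose and dose-proportional kinetics, both stated in the protocol.

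The size is illustrative: a slope standard error about 3.1 to 1.5 times larger for an assumed CV of 20% to 50%, under a linear model with zero-exposure placebo. Exposure-response lies outside the fixed testing sequence, and no primary, key secondary or safety comparison changes. Separately, SAP 15.2 omits the key secondary endpoints that Protocol 2.6.1 lists, and Section 19 does not declare it. Both points should be corrected; neither threatens the trial's main results.

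**What to change.** 1. In SAP Section 15, confine the PK Analysis Set and the two-arm grouping to the concentration summaries of Section 15.1.
2. In Section 15.2, and carried into the separate PK/PD plan, define the exposure-response population. For efficacy: Full Analysis Set subjects on placebo at zero exposure, with Full Analysis Set subjects on ACP-044 who have at least one evaluable concentration. For TEAEs: the same rule in the Safety Analysis Set.
3. Add an active-only fit as a sensitivity analysis. It shows how far the result depends on the placebo anchor and on the assumed shape between zero and the observed exposures.
4. Restore the key secondary endpoints in Section 15.2 to match Protocol 2.6.1, or declare and justify the change in Section 19.

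The cost is SAP wording and a small amount of extra analysis. Placebo subjects need no concentration data for this, and their pain and TEAE data are already collected.

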15.1 Pharmacokinetic Endpoints

The PK endpoints of the study are:

- Plasma concentrations of ACP-044 for a total of six (6) samples: Day -1 (predose), Day 1 (one sample taken between 2-3 hours and one sample taken between 4-6 hours, after the first dose of the day), Day 2 (prior to the first dose of the day), and Day 3 (one sample taken between 2-6 hours and one sample taken between 8-12 hours, after the first dose of the day)
- ACP-044 PK parameters determined using a population PK approach

Plasma concentration of ACP-044 will be summarized by treatment group using the Pharmacokinetic Analysis Set.

PK parameter summary and analysis will be discussed in a separate plan.

15.2 Pharmacokinetic/Pharmacodynamic Endpoints

The PK/PD endpoints include:

- ACP-044 exposure-response relationship:
 - for efficacy using the primary endpoint and selected secondary endpoints
 - for safety using selected TEAEs

PK/PD endpoint summary and analysis will be discussed in a separate plan.

16 INTERIM ANALYSIS

No interim analyses are planned for this study.

17 DATA MONITORING/REVIEW COMMITTEE

There is no data monitoring/review committee in this study.

18 COMPUTER METHODS

Statistical analyses will be performed using Version 9.4 (or newer) of SAS® (SAS® Institute, Inc., Cary, North Carolina) on a suitably qualified and validated environment.

Validation and quality control of the tables, listings and figures containing the results of the statistical analyses will follow appropriate standard operating procedures.

19 CHANGES TO ANALYSES SPECIFIED IN PROTOCOL

None.

21 APPENDICES

21.1 Schedule of Events and Assessments

	Screening Period	Double-blind Treatment Period							Unscheduled Visit ^m	Safety Follow-up Period	
		Day -1 (Dosing and Postdose)	Day 1 (Time 0)	Day 2	Day 3	Day 4 (EOT/ET)	Clinic visit	Telephone call			
Visit Day	-28 to -2	Day -1 Predose							7 days after EOT	30 days after last dose	
Visit window (# days)		0	0	0	0	0			±3	+4	
Informed consent	X										
Inclusion/exclusion criteria	X	X									
Medical and surgical history and demographics	X										
Physical examination	X	X					X ^k		X ^k		
Vital signs ^a	X	X		X	X	X	X	X			
Height, weight ^b	X	X									
12-lead ECG ^c	X	X		X	X	X	X				
Clinical laboratory tests	X	X					X				
Pregnancy test ^d	X	X									
Urine toxicology screen	X	X									
COVID-19 test ^e	X	X									
Clinic check in/out			X				X				
Randomization		X									
Study drug administration			X	X	X	X					
Pain assessment training ^f	X	X									
Bunionectomy			X								
Block Quality Assessment ^g			X								
11-point Numeric Rating Scale (NRS) of pain intensity ^h				X	X	X	X				
Foot and Ankle Ability Measure		X							X		
Rescue medication ⁱ				X	X	X	X				

